In the recent years there is a gradual upward trend in day care surgeries all across the globe; an estimated 83% of the surgeries in the United States being performed on an ambulatory basis¹. In India, about 20 percent of all surgical procedures are performed on outpatients. It is estimated that by 2020, 75 percent of all surgical operations in India will be carried out in ambulatory surgery centers². The increasing trend of ambulatory surgeries has emerged from advances in anesthesia and surgical techniques. Patient information and effective communication is critical in these surgeries especially the ones that need General Anesthesia. Provision of information is one of the mainstays of effective day surgery management. This needs to cover not only what to do preoperatively and postoperatively, but also what will happen on the day of surgery. There are several ways of providing information like written information, using a video, over telephone or by patient interviews before and

after surgery. Verbal information alone is inadequate and must be reinforced with well-presented printed material³.

Tata Memorial hospital is a premier tertiary level cancer hospital in India. Around 140-150 patients undergo minor surgical procedures (diagnostic and therapeutic) in our hospital's Minor OT complex every day. About 30-40% of surgeries belong to the Head & Neck region alone. About 40-50% of these surgeries are done under General Anaesthesia. At present the communication with patients in the busy outpatient department is mainly verbal. Due to time constraints, lack of a responsible attendant with the patient, important information with respect to the day care procedure is often not effectively delivered. This leads to patients not following instruction adequately with respect to starvation, medications to be taken on the day of the procedure and also not carrying all essential documents. This leads to delays, rescheduling of cases and rarely postponement of procedures.

Does an information leaflet provide an effective way of communication in the peri-procedure period? Will it help in better information delivery and hence reduce the number of avoidable postponements and delay. And does this translate to better patient satisfaction is what this study aims to see. The study is restricted to patients undergoing Head & Neck procedures under General Anaesthesia, as they form the major bulk of patients in our minor OT complex and for logistic reasons to start with a defined group of patients.

AIMS AND OBJECTIVES:

1. To reduce postponement of cases due to lack of information to patients in the pre-operative period
2. To compare satisfaction levels between patients , pre and post introduction of information leaflet

Primary end point:

To reduce postponement of cases due to lack of information to patients in the pre-operative period

Co Primary end point:

To compare satisfaction levels between patients, pre and post introduction of information leaflet.

Design of the study: Pre and post interventional model

INCLUSION CRITERIA:

All adult patients (> 18yrs), ASA I-III, undergoing elective therapeutic/diagnostic Head & Neck surgeries under General Anaesthesia in the Minor OT complex and discharged on the same day will be included. The surgeries will include Head & Neck surgeries like DL scopes, laser surgeries, EUA, excision biopsies etc.

EXCLUSION CRITERIA:

1. Patients refusing to take part in study
2. Patients undergoing emergency surgeries
3. ASA IV patients, or high risk patients planned for admission
4. Admitted patients for minor OT procedure
5. Patients not getting the Information leaflet due to any reason (in 2nd half of study)
6. Patient and his attendant, both illiterate

MATERIAL AND METHODS

After Institutional Review Board approval, all adult patients meeting inclusion criteria and undergoing surgeries in the Minor OT complex during a 6 month period will be enrolled in the study. The study will be done in two parts.

In the First half of study- planned over 2 months (Nov-Dec), feedback forms will be collected from patients at the end of minor OT procedure (Annexure 2.1) All patients, meeting inclusion criteria, at the end of the procedure prior to discharge from the minor OT will be explained about the study and they shall be given a feedback form to be filled and submitted. Also the number of postponement or rescheduling of cases will be noted.

Postponement or rescheduling of case is defined as an event when the patient who is called for his turn in minor OT is deferred for any amount of time in account of starvation not adequate, investigations not brought, medications not taken as prescribed. Any postponement in view of awaiting opinion from senior consultant , special equipment or any investigations called in view of patients clinical conditions which was not anticipated in the OPD by the surgical colleague, or due to lack of OT time will not be included.

After the initial collection of feedback over 2 months, the patient information leaflet (PIL) will be handed over to all patients planned for procedure in the minor OT complex (Second half of study). This leaflet will be handed over by the attending doctor in the Head neck OPD. The checklist pertaining to counselling at the Head neck OPD will be ticked after they are carried out. The patient will be instructed to read leaflet carefully and carry the leaflet on the day of Minor OT procedure. In the minor OT the discharge checklist in the PIL would be carried out by all concerned including the surgical, anesthesia and nursing team. A period of 1 month (Jan) will be allowed to streamline the use of patient information leaflet.

In the subsequent 2 months, Feb - Mar, the impact of use of PIL will be assessed. Firstly by noting the number of postponement or rescheduling of cases. In addition all patients meeting inclusion criteria will be given the feedback form (Annexure 2.2) at the end of their procedure in minor OT.

For patients coming to minor OT without a patient information leaflet- one would ascertain if the leaflet was handed in OPD and not brought to minor OT or if the leaflet was not handed at all. The numbers of such misses will be recorded. Patients who did not get the leaflet in the OPD will be excluded from study.

Sample size calculation:

For our preliminary review of postponement rate as defined in our study is around 20%. We aim for a reduction of such postponement by 50%. Group sample sizes of 199 in group 1 and 199 in group 2 achieve 80.007% power to detect a difference between the group proportions of -0.1000. The proportion in group 1 (the treatment group) is assumed to be 0.2000 under the null hypothesis and 0.1000 under the alternative hypothesis. The proportion in group 2 (the control group) is 0.2000. The test statistic used is the two-sided Z-Test with pooled variance. The significance level of the test is 0.0500. Considering a 20% loss to follow up from OPD to minor OT, the sample size needed is 480 patients. On an average at least 250 patients of head neck patients undergo procedure under general anesthesia, per month (12-15 patients /day x 20 working days). With due consideration of our inclusion criteria, a two month recruitment period pre and post intervention should be adequate.

MEASUREMENTS

- No. of cases postponed pre and post introduction of the leaflet and reasons behind them
- Primary data collected will be patient satisfaction levels after the procedure (both pre and post PIL) on a 5 point Likert scale (Ranging from very poor = 0 to Excellent = 4)
- No of patients who did not receive the patient information leaflet in the OPD
- No of patients who received the PIL but did not get it along to the minor OT

STATISTICAL ANALYSIS

All Data will be analyzed using SPSS software. Likert scores will be treated as ordinal data. Proportions will be compared using chi square analysis. Additionally Multivariate logistic regression analysis will be used to assess the contribution of possible covariates, including age sex and patient knowledge on patient satisfaction. For all data P-value < 0.05 will be considered as statistical significant.

REFERENCES:

1. Beverly K. Philip MD, Day Care Surgery: The United States Model of Health Care IAAS Journal/17.4/PHILIP17.4.pdf
2. Emerging Trends in Healthcare A Journey from Bench to Bedside 17 February 2011;KPMG/ASSOCHAM
3. Jarrett, P. E. M, Day care surgery ;European Journal Of Anaesthesiology November 2001 - Volume 18 - Issue - p 32–35

Annexure 2.1

You are invited to take part in this study & help us improve the quality of services provided to you. Your participation is completely voluntary & it will not alter the treatment given to the patient in any way. Please base your answers on today's experience at this MINOR OT COMPLEX. Just mark the option which the patient thinks is correct.

1. Patients age _____ Gender _____

2. Education: Illiterate/ school/ graduate/ post graduate (please tick patients highest qualification)

3. Are you filling this questionnaire for self or on behalf of the patient?,

If Yes (please tick your highest qualification) Education Illiterate/ school/ graduate/ post graduate

4. Is this your first visit to this Minor OT complex? Yes No

If "No" when was the last time you came here? _____

5. Were you adequately informed with regard to the fasting procedure, pre-surgery (What to eat/drink)?

Yes No Not sure

6. Were you informed about any tests (blood tests, ecg, scans,x-ray etc.) that were necessary before the procedure?

Yes No Not sure

7. If you take any medicine on a regular basis, were you informed about which medicines to continue or to avoid on the day of surgery?

Yes No Not sure

8. Did you receive enough information about the future course of action about your treatment (includes when to expect the result of today's procedure, future treatment & follow up)

Yes No Not sure

9. How was your overall satisfaction with respect to the information you were provided before the surgery?

Excellent Very good Good Poor Very Poor

10. How was your overall satisfaction with respect to the information you were provided after the surgery?

Excellent Very good Good Poor Very Poor

Annexure 2.2

You are invited to take part in this study & help us improve the quality of services provided to you. Your participation is completely voluntary & it will not alter the treatment given to the patient in any way. Please base your answers on today's experience at this MINOR OT COMPLEX. Just mark the option which the patient thinks is correct.

1. Patients age _____ Gender _____

2. Education Illiterate/ school/ graduate/ post graduate (please tick patient's highest qualification)

3. Are you filling this questionnaire for self or on behalf of the patient? If Yes (please tick your highest qualification) Education Illiterate/ school/ graduate/ post graduate

4. Is this your first visit to this Minor OT complex?, Yes No

If "No" when was the last time you came here? _____

5. Were you adequately informed with regard to the fasting procedure, pre-surgery (What to eat/drink)?

Yes No Not sure

6. Were you informed about any tests (blood tests, ecg, scans,x-ray etc.) that were necessary before the procedure?

Yes No Not sure

7. If you take any medicine on a regular basis, were you informed about which medicines to continue or to avoid on the day of surgery?

Yes No Not sure

8. Did you receive enough information about the future course of action about your treatment (includes when to expect the result of today's procedure, future treatment & follow up)

Yes No Not sure

9. Have you received any Information leaflet at the OPD?

Yes No

If "yes "have you read the leaflet?

Yes No

If "yes "have you understood the information provided in the leaflet?

Yes No

10. What is your opinion about the leaflet?

Very Good Good Average Bad Very Bad

11. Would you recommend this leaflet to others?

Strongly recommend / will Recommend/ Neutral /recommend reluctantly/ not recommend at all

12. How was your overall satisfaction with respect to the information you were provided before the surgery?

Excellent Very good Good Poor Very Poor

13. How was your overall satisfaction with respect to the information you were provided after the surgery?

Excellent Very good Good Poor Very Poor

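### Patients who miss the leaflet are excluded from the after-period only, so the two periods are selected differently and can differ with no leaflet effect

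*Combined protocol and SAP*

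**What the plan says.** The study compares two periods, November-December before the leaflet and February-March after it. Material and Methods states that "all adult patients meeting inclusion criteria and undergoing surgeries in the Minor OT complex during a 6 month period will be enrolled". For the after-period only, Exclusion Criteria item 5 removes "Patients not getting the Information leaflet due to any reason (in 2nd half of study"). The account of the second half in Material and Methods confirms it: "Patients who did not get the leaflet in the OPD will be excluded from study".

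On non-recipients the plan asks for a count: "The numbers of such misses will be recorded", and Measurements lists the same number. Measurements also lists "No. of cases postponed pre and post introduction of the leaflet and reasons behind them", without saying whether excluded patients contribute. Statistical Analysis compares proportions by chi-square and describes a regression for satisfaction only. It states no all-patients analysis and no sensitivity analysis.

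The leaflet is meant to reach every patient planned for a procedure, and "A period of 1 month (Jan) will be allowed to streamline the use of patient information leaflet" before the after-period data are collected. In the two months that follow, "the impact of use of PIL will be assessed".

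**The concern.** A before-after comparison needs both periods to contain the same kind of patient. Here the patients who would miss a leaflet stay in the before-group, where they cannot be identified, and are taken out of the after-group. If their postponement risk differs from that of other patients, the after-period rate moves with no leaflet effect. A change between periods could then reflect the leaflet, the selection, or both, and no planned analysis separates the two. Satisfaction, the co-primary endpoint, is exposed in the same way.

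The introduction makes one direction plausible. The sentence beginning "Due to time constraints, lack of a responsible attendant with the patient, important information" goes on to say that information often fails to reach patients, and the text then links this to delay and rescheduling. If the same pressures cause missed leaflets, the excluded patients would be at higher risk and the bias would favour the leaflet. The documents do not say who would miss a leaflet, so this remains a possibility.

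**Working it through.** **Inputs from the Sample size calculation.** Before-rate 0.20, target rate 0.10, 199 per group, two-sided pooled Z-test, alpha 0.05, planned total 480, at least 250 patients a month.

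**Assumed inputs.** The share missed, f, and the postponement rate in missed patients, r. The documents give neither, so a range is shown.

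**Reproducing the plan's figure.** With rates p1 and p2 and mean p̄:

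- SE0 = √[2p̄(1−p̄)/n] and SE1 = √[(p1(1−p1)+p2(1−p2))/n]
- For 0.20 against 0.10 at n = 199: SE0 = √(2×0.15×0.85/199) = 0.03580 and SE1 = √(0.25/199) = 0.03544
- Power = Φ[(0.10 − 1.96×0.03580)/0.03544] = 0.80007, as the plan states

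**Selection with no leaflet effect.** The true rate is 0.20 in both periods. Among the recipients who are kept, the rate is q = (0.20 − f×r)/(1 − f). For f = 0.20 and r = 0.40, q = (0.20 − 0.08)/0.80 = 0.150. The chance of p<0.05 is the two-tailed rejection probability for 0.20 against q at 199 per group.

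| Share missed f | Rate in missed r | Rate kept q | Chance of p<0.05 |
|---|---|---|---|
| any | 20% | 20.0% | 5.0% |
| 2% | 40% | 19.6% | 5.1% |
| 5% | 40% | 18.9% | 5.8% |
| 10% | 30% | 18.9% | 5.9% |
| 10% | 40% | 17.8% | 8.7% |
| 20% | 30% | 17.5% | 9.8% |
| 20% | 40% | 15.0% | 25.9% |
| 10% | 10% | 21.1% | 5.9% |
| 20% | 10% | 22.5% | 9.3% |

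In the last row, 8.8 of the 9.3 percentage points are against the leaflet. If all eligible patients are kept, q is not used and every row is 5.0%.

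**Price of keeping everyone.** Suppose the leaflet halves the rate in recipients and does nothing in non-recipients. The after-rate is (1−f)×q/2 + f×r, which at equal risk is 0.10(1−f) + 0.20f. The 240 column (480/2) assumes that all 240 per group are analysed, so that none of the 20% loss allowance is used up.

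| f | r | After-rate | Power, 199 per group | Power, 240 per group | n per group for 80% |
|---|---|---|---|---|---|
| 5% | 20% | 10.5% | 75% | 83% | 224 |
| 10% | 20% | 11.0% | 70% | 78% | 253 |
| 20% | 20% | 12.0% | 59% | 67% | 329 |
| 10% | 30% | 11.5% | 64% | 73% | 288 |
| 20% | 30% | 13.0% | 47% | 54% | 441 |
| 20% | 40% | 14.0% | 36% | 42% | 615 |

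At equal risk and 240 per group, 80% power holds up to about 8% missed.

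**Satisfaction.** The documents give no satisfaction distribution, so this part cannot be sized.

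**The case against.** The best counter-argument is that misses may be rare. The attending doctor hands the leaflet to every patient, an outpatient checklist is ticked, and January is set aside as a run-in. At 2% to 5% missed, the table shows almost no inflation. The 25.9% row needs one patient in five missed after the run-in, with a postponement rate of 40% against 15% in recipients. This stands, and that row should not carry the argument. But the plan states no expected miss rate, and it provides an exclusion, a tracking step and a measurement for misses.

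Second, the aim may be the effect of using the leaflet, which would make recipients the right group. That does not repair the comparison, because the before-group is unfiltered under that reading too.

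Third, some data on non-recipients may be collected anyway. Annexure 2.2 item 9 allows the answer No, and the postponement tally is not expressly limited to recipients. That may be so, but these patients are excluded from the study and no analysis of them is stated.

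Fourth, keeping everyone costs power, and the cost is greatest where the bias is greatest. This stands. So does the point that other changes between the two periods remain possible explanations in an uncontrolled before-after design. Removing the exclusion deals with this one selection difference only.

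**Conclusion.** The concern holds and should be fixed. The asymmetry is certain, since it is written twice and has no counterpart in November-December. Its consequence is conditional. The bias is negligible if few leaflets are missed, zero if missed patients have the same risk as others, in favour of the leaflet if they are at higher risk, and against it if they are at lower risk. Over the assumed values shown, the chance of a significant result with no leaflet effect runs from 5.0% to 25.9%. These figures assume a true rate of 20% in both periods and 199 per group. The documents do not show where in that range the trial would fall.

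**What to change.** Before November-December starts:

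- Delete exclusion 5 and the matching sentence in Material and Methods.
- Define the primary comparison as all otherwise eligible patients in February-March against November-December, regardless of leaflet receipt.
- Record postponement in non-recipients as well as their number.
- Keep the recipients-only comparison as supportive.
- On Annexure 2.2, let patients who answer No to item 9 skip items 10 and 11.
- Enrol all eligible patients in both periods, as the plan already provides, because the before-period cannot be enlarged later.
- Restate power over a range of miss rates, for example 5%, 10% and 20%.

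The drafting cost is two deletions, one sentence on the analysis set, one added record for patients already identified in the minor OT, and a revised power statement. The real cost is the dilution shown above. The stated flow of at least 250 a month gives about 2 × 250 = 500 per period before eligibility losses. That may cover 224 to 329 per group, perhaps 441, but not 615.

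A smaller alternative keeps recipients-only as primary, prespecifies the all-patients comparison, and reports postponements in non-recipients. This exposes the selection but leaves it in the primary test.

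### The primary postponement rate has no stated denominator, and some enrolment rules, if applied to it, would select patients after the outcome has occurred

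*Combined protocol and SAP*

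**What the plan says.** **Event.** Material and Methods defines postponement or rescheduling as arising when "the patient who is called for his turn in minor OT is deferred for any amount of time" because of inadequate starvation, missing investigations or medication not taken as prescribed.

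**Recording.** For the first half: "Also the number of postponement or rescheduling of cases will be noted". The second half likewise notes a number, and Measurements lists the number of cases postponed with reasons. No count of patients called is listed.

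**Analysis.** The sample size section assumes a postponement rate of about 20%, to be halved. Statistical Analysis compares proportions by chi-square. Neither names a denominator.

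**Who is enrolled.** Material and Methods: "all adult patients meeting inclusion criteria and undergoing surgeries in the Minor OT complex during a 6 month period will be enrolled". The inclusion criteria cover patients operated "under General Anaesthesia in the Minor OT complex and discharged on the same day will be included". Exclusion 1 is "Patients refusing to take part in study". For the first half, "All patients, meeting inclusion criteria, at the end of the procedure prior to discharge from the minor OT will be explained about the study".

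**Two further exclusions.** Exclusion 5 is "Patients not getting the Information leaflet due to any reason (in 2nd half of study"). Leaflet status is checked when the patient comes to the minor OT, and misses are recorded. Exclusion 6 is "Patient and his attendant, both illiterate".

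**The concern.** A proportion needs a numerator and a denominator drawn from the same defined set. Here the outcome happens at the call, while three of the enrolment conditions are or may be settled later: surgery performed, same-day discharge, and agreement to take part. If they govern the primary endpoint, a patient who is called, deferred and not operated on within the period leaves the analysis because of the outcome itself.

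In an unblinded before/after study, an unstated denominator also means that the rate can be computed in more than one way, with the choice made after the counts are known. A count of patients called may not be recoverable later if nobody logs it.

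Exclusion 5 raises a separate comparability problem. It removes patients from the second period on a condition that has no counterpart in the first.

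**Working it through.** **1. The plan's own figure.** Inputs from the sample size section: 20% v 10%, 199 per group, two-sided pooled Z-test, alpha 0.05.

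- Pooled proportion 0.15. Standard error under the null: √(2 × 0.15 × 0.85 / 199) = 0.0358.
- Standard error under the alternative: √((0.20 × 0.80 + 0.10 × 0.90) / 199) = 0.0354.
- Power = Φ((0.10 − 1.96 × 0.0358) / 0.0354) = 80.0%.

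This agrees with the stated 80.007%. The per-group calculation is not in question.

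**2. When each condition is settled.**

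| Condition | Settled |
|---|---|
| Age, ASA class, elective status, planned admission | Before the call |
| Leaflet given (second half only) | In the OPD; checked on coming to the minor OT |
| Undergoing surgery | After the call, if read as surgery performed |
| Same-day discharge | After the call, unless it only means day-case |
| Refusal | End of the procedure in the first half |
| Both illiterate | Timing not stated; the education item shown is on the post-procedure form |

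**3. Effect of applying the later rules.** Let s be the share of postponed patients lost in excess of other patients. The documents give no value; 5% and 10% are assumed. I also assume that the preliminary 20% was measured among patients called.

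Rate among those retained = p(1 − s) / (1 − ps).

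- s = 5%: 0.19/0.99 = 19.2% and 0.095/0.995 = 9.5%.
- s = 10%: 0.18/0.98 = 18.4% and 0.09/0.99 = 9.1%.

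At 199 called per group, 39.8 and 19.9 postponed patients are expected. The loss is then 2.0 and 1.0 patients (s = 5%) or 4.0 and 2.0 (s = 10%).

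Power below assumes that 199, or 240 (480/2), patients are analysed per group.

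| s before, after | Rates | Difference | Power, 199 | Power, 240 |
|---|---|---|---|---|
| 0, 0 | 20.0% v 10.0% | 10.0 points | 80.0% | 86.8% |
| 5%, 5% | 19.2% v 9.5% | 9.6 | 78.5% | 85.6% |
| 10%, 10% | 18.4% v 9.1% | 9.3 | 76.9% | 84.2% |
| 5%, 10% | 19.2% v 9.1% | 10.1 | 82.7% | 89.0% |
| 10%, 5% | 18.4% v 9.5% | 8.8 | 72.0% | 79.8% |

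Restoring 80% power under equal loss takes 207 (s = 5%) or 215 (s = 10%) per group.

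**4. No true effect (20% in both periods).** Equal s gives equal rates, so the null is unbiased. With s of 5% then 10%, the rates are 19.2% v 18.4%, and at 199 per group the test rejects 5.5% of the time instead of 5%.

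**5. Exclusion 5.** The number of patients without a leaflet and their postponement rate are not given, so no size can be computed.

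**The case against.** **The intended set can largely be inferred.** The event is tied to the call, the 20% is described as following the study's own definition, and postponements are noted separately from the feedback form in both periods. Nothing limits the count to patients who return a form. Same-day discharge can mean day-case, which fits the exclusions of planned admissions and inpatients, and undergoing surgery can describe the booked population. This stands as the more natural reading. But it defines the event and not the base, and the written enrolment rules are the only ones the plan gives.

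**Most eligibility rules precede the call.** A reader might infer that the whole enrolled set is defined after the outcome. The documents do not support that: age, ASA class, elective status and planned admission are fixed earlier, and the leaflet is given or missed in the OPD. Only the three conditions named above are in doubt.

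**The effect is small.** The Introduction calls outright postponement rare, and the event counts a deferral of any length. Patients merely delayed that day can still complete and need not be lost. If all 480 patients were analysed, power would stay near or above 80% in every scenario above. This stands, and it limits the point to its size.

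**Literacy could be asked earlier.** A reader might infer that exclusion 6 can be applied only from the post-procedure form. The form is the only place shown where education is recorded, but the plan does not rule out asking in the OPD or on arrival.

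**Counting each patient once is a preference.** Agreed. Counting cases is also defensible; what matters is that the unit is fixed in advance.

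**Conclusion.** The point holds as a gap in the definition of the primary endpoint, with a probably small numerical consequence. No denominator is stated, and following the written enrolment rules literally would select on events after the outcome.

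Equal excess loss leaves the null unbiased but shrinks a true difference from 10.0 points to 9.6 or 9.3. Unequal loss can also bias the null slightly. These figures rest on assumed losses of 5% to 10% and on the preliminary 20% having been measured among patients called. If it already came from completed cases, the equal-loss fall in power does not arise.

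Two stronger readings are not supported. One is that the plan will analyse completers only: the text permits this but does not say it. The other is that exclusion 5 makes the two periods differ whichever set is used: it does so only when applied, and disappears if all patients called are counted. Where it is applied, the comparison loses some patients from one period only, by an amount that the documents do not allow to be sized.

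**What to change.** Add an analysis-set paragraph for the primary endpoint:

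- **Set:** in both periods, all otherwise eligible elective adult Head & Neck day-case patients under general anaesthesia who are called for their turn in Nov-Dec or Feb-Mar, regardless of completion, actual same-day discharge or form return.
- **Unit:** stated in advance, for example each patient once at the first call in the period.
- **Completion and form refusal:** applied to the satisfaction endpoint only.
- **Log:** number called and number postponed in each period.
- **Exclusion 5:** record postponement status for second-half patients without a leaflet, and report the primary rate with them included.
- **Exclusion 6:** apply it to the primary endpoint only if literacy is ascertained the same way in both periods, independently of form return.

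The cost is a simple log of patients called and one extra analysis. Leaflet misses are already to be recorded, so only postponement status is added for those patients. If exclusion 6 is kept for this endpoint, a literacy entry is needed for patient and attendant. The ethics board may need to agree to the use of de-identified counts for patients who do not fill in the form.

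### The only satisfaction form is given after the procedure, so a patient sent away to another day never rates the failed visit; who answered, and whether before discharge advice, is also unclear

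*Combined protocol and SAP*

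**What the plan says.** **Timing.** Under Material and Methods, first-half patients "at the end of the procedure prior to discharge from the minor OT will be explained about the study" and are given the form of Annexure 2.1. For February-March, "all patients meeting inclusion criteria will be given the feedback form (Annexure 2.2) at the end of their procedure in minor OT". One form per patient is described, and none when a case is deferred.

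**Reference period.** Both annexures open with an invitation to take part and the instruction "Please base your answers on today's experience at this MINOR OT COMPLEX".

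**Postponement.** A case counts when the patient, called for their turn, is "deferred for any amount of time in account of starvation not adequate, investigations not brought, medications not taken as prescribed". This covers a short same-day delay as well as a move to another date. The introduction lists delays and rescheduling as the usual consequences of poor information and describes outright postponement as rare.

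**Endpoint.** Satisfaction before versus after the leaflet is co-primary. The forms ask separately about information given before surgery (item 9 in Annexure 2.1, item 12 in Annexure 2.2) and after surgery (items 10 and 13). Items 5-7 cover fasting, tests and medicines; item 8 covers the future course of treatment.

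**Respondent.** Item 3 asks "Are you filling this questionnaire for self or on behalf of the patient" and continues with an instruction that applies if the answer is yes.

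**The concern.** The leaflet is meant to prevent patients arriving unprepared. The clearest failure is a patient sent home to return another day. That patient reaches the end of a procedure only on the second attempt, when the fault has been put right, and is then asked about that day. The rating of the failed visit is never taken. If the patient does not come back, there is no rating at all.

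This does not fall equally on the two periods. If the leaflet reduces such deferrals, the before period has more of them. Its satisfaction is then raised more than that of the after period, and the co-primary difference shrinks.

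Two smaller faults come from the same form:

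- The trigger is the end of the procedure, not the end of discharge counselling. In the second half the leaflet's discharge checklist is carried out in the minor OT, so it is part of what is being tested. A form filled in before the checklist could not credit it.
- Attendants are expected to answer for some patients, since the exclusion applies only when patient and attendant are both illiterate. An either/or question followed by a yes-branch does not reliably show which of them answered.

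**Working it through.** **The plan's own figure.** For 20% versus 10%, with a two-sided pooled Z-test at alpha 0.05 and 80% power:

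n = [1.960 × √(2 × 0.15 × 0.85) + 0.842 × √(0.2 × 0.8 + 0.1 × 0.9)]² / 0.10² ≈ 199 per group.

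The stated 199 and 80.007% reproduce. Nothing below disputes them; they supply the deferral rates and group size.

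**Inputs.**

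- From the sample size section: postponement 0.20 before and 0.10 after; 199 per period.
- Assumed: 60% of deferred patients would rate pre-surgery information poor or very poor on the visit where they were deferred, against 10% of all others.
- Assumed: a patient moved to another day who returns rates the corrected visit like the others, at 10%.
- Not given, so varied: f, the share of postponements moved to another day.

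**If every deferred patient rated the visit that failed.**

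- Before: 0.8 × 0.10 + 0.2 × 0.60 = 0.20
- After: 0.9 × 0.10 + 0.1 × 0.60 = 0.15
- Gain: 5 percentage points

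**With the form as planned.** A fraction f of the deferred drops from 0.60 to 0.10:

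- Before: 0.20 − 0.2f × 0.50 = 0.20 − 0.10f
- After: 0.15 − 0.1f × 0.50 = 0.15 − 0.05f
- Gain: 0.05 − 0.05f, a loss of 5f points

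| f | Patients affected, before v after (199 × 0.2f v 199 × 0.1f) | Observed dissatisfaction, before v after | Gain (points) | Loss (points) |
|---|---|---|---|---|
| 5% | about 2 v 1 | 19.5% v 14.75% | 4.75 | 0.25 |
| 25% | about 10 v 5 | 17.5% v 13.75% | 3.75 | 1.25 |
| 50% | about 20 v 10 | 15.0% v 12.5% | 2.5 | 2.5 |
| 100% | about 40 v 20 | 10.0% v 10.0% | 0 | 5 |

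**If those patients never return.** They leave the denominator too. At f = 50%, before is (0.08 + 0.10 × 0.60)/0.90 = 0.156 and after is (0.09 + 0.05 × 0.60)/0.95 = 0.126. The gain is 2.9 points, a loss of 2.1, so the effect is similar to that of rating the corrected visit.

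**On the 0-4 scale.** If each affected patient scores the corrected visit 1 point higher (assumed), the difference in means shrinks by (0.2f − 0.1f) × 1 = 0.1f: from 0.005 at f = 5% to 0.10 at f = 100%.

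**Respondent and order.** No arithmetic applies. Item 2 records the patient's education and item 3 has a second education line. A tick there suggests an attendant, but a patient could also tick it and an attendant could leave it blank. The planned regression names age, sex and patient knowledge, not respondent type. For the after-surgery items, Material and Methods gives the form's trigger and mentions the discharge checklist, but does not order them.

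**The case against.** **The effect may be slight.** Same-day deferrals are still rated on the day of the delay, so they are unaffected. The 20% rate includes them, and the introduction calls outright postponement rare. The 60% and 10% are not from the documents. This stands, and it is why the result is given as 5f. A reader might infer that the gain vanishes, or that the co-primary endpoint omits the worst-informed patients as a class. The first needs every deferral to be to another day. The second fails because same-day deferrals and returners do get a form; only non-returners are missing.

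**The bias is conservative.** It hides benefit and cannot by itself create it. True, but a co-primary comparison should not be blunted when a short form avoids it.

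**The items are broad enough.** The satisfaction item concerns information before surgery, which could take in the earlier visit, and item 4 asks about previous visits. This helps to spot returners. But the instruction points to the day itself, and by then the information received includes the correction.

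**Recovery from anaesthesia.** Because everyone is "under General Anaesthesia in the Minor OT complex and discharged on the same day will be included", a reader might infer that all are approached, and agree to take part, while still recovering. The documents do not support this. The stated window runs up to discharge, so it includes the time when a patient is ready to go home. Consent pages are not in the copy reviewed. For the second half only the form is timed; a late invitation is inferred from the form's own wording. Any such effect would apply to both periods.

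**Order of form and counselling.** A reader might infer that forms are completed before discharge advice. Nothing says so; the trigger merely permits it.

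**Conclusion.** The point holds as a correctable weakness in how the co-primary endpoint is collected. Patients moved to another day for an information failure give no rating of the visit that failed, and non-returners give none at all. If the leaflet reduces such deferrals, the comparison is biased against it.

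The size is not known. Under the assumed 60% and 10%, with returners rating like everyone else, the loss is 5f points of a 5-point gain. It is a quarter of a point if one postponement in twenty goes to another day and half the gain if one in two does. The introduction's wording suggests the lower end but gives no figure. The sample size calculation for postponement is unaffected.

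The loose order of form and discharge instructions, and the ambiguous item 3, are secondary. They add avoidable uncertainty about what the after-surgery items measure and whose opinion is recorded. Neither is shown to have caused bias.

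**What to change.** Apply the same procedure in both periods.

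1. **At deferral to another day.** Once the postponement has been recorded, have the patient complete items 5-7 and the before-surgery satisfaction item at that visit. State in the analysis section whether this rating enters the main before/after comparison or a named sensitivity analysis. Mark each postponement as same-day or other-day, so that f can be reported.
2. **Everyone else.** Keep the post-procedure form, but hand it over once discharge instructions (second half: the discharge checklist) are complete.
3. **Item 3.** Replace it with two tick-boxes, patient or attendant, followed by the attendant's education.

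Items 5-7 should not be moved to arrival. Asking about fasting, tests and medicines before the patient is called could bring problems to light early and so change the primary postponement endpoint.

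**Cost.** The change needs a form edit, a handover rule and a short extra form for patients sent away: at f = 25% and 199 per period, about 10 + 5 = 15 in all. The drawback is that these patients rate pre-surgery information at a different time point from the rest, which should be acknowledged when results are reported.
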